2.2.2 Secondary Endpoints

Tolerability - 75% of patients will be able to tolerate trial medication, in at least half dose, up to one year after randomisation (i.e. less than 25% will stop trial medication completely through inability to tolerate the drugs).

Safety - symptoms of systemic or intracranial bleeding, recurrent cerebral and systemic vascular events, and vascular and non-vascular causes of death will be collected. The absolute risk of death, including fatal haemorrhage, will not differ significantly (ie fall outside the upper 95% CI) from 2% per year on trial drugs versus no trial drugs, when given in addition to guideline drugs; and will not increase bleeding or ischaemic SVD lesions significantly (at the p<0.01 level) on MRI.

Efficacy – individual event-rate data (stroke, TIA, myocardial ischaemia, cognitive impairment and dementia, will be collected. The *combined rate* of recurrent stroke, MI, death, cognitive impairment and dependency will be 40-50% at one year after enrolment in order to detect modest but clinically-important reductions in poor outcomes.

Health Economics – data to assess health economic impact will be gathered.

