8b Secondary Objectives: To assess drug tolerability, safety, recruitment rates and accuracy, outcome event rates and retention in preparation to a large phase III randomised controlled trial to prevent recurrent lacunar stroke and physical and cognitive impairment.

This SAP focuses on these primary and secondary objectives. Planned follow-on publications will address tertiary questions.

SECTION 3. STUDY METHODS

9 Trial design

Prospective randomised open-label blinded end-point (PROBE) partial-factorial phase IIb/c trial aiming to recruit 400 patients recruited in UK Stroke Network Centres, with follow-up to one year.

10 Randomisation: By central computer-generated allocation at the University of Nottingham with minimisation on key prognostic factors: age, sex, stroke severity (NIHSS), dependency resulting from the stroke, systolic blood pressure $\leq/ > 140$ mmHg, smoking status, time after stroke, and years of education.

11 Sample size/power considerations

Conservatively, we have used sample size calculations based on binary measures. Use of ordinal measures at the time of analysis will increase statistical power.

11a Event rates: Annual event rates (Table A) were assessed from trials (SPS3,⁵ lacunar patients in ENOS,^{6 7} IST-3^{8 9}) and observational data (LADIS;¹⁰ our¹¹⁻¹³ and other¹⁴ studies). All-cause death rates were assumed to be 2.0% with upper 95% CI of 4% in 400 patients.⁵ Hence, the sample size was set at 400 participants.

Table A Annual absolute risks (%) of outcome events after lacunar stroke

Vascular death	Non-vascular death	Non-fatal IS or TIA	Non-fatal ICH	MI	MACE	Dependent (mRS 3-5)	Cognitive impairment	Dementia
1.8	0.5	2.5	0.5	0.6	3	15	30	15

ICH: intracerebral haemorrhage; IS: ischaemic stroke; MACE: major adverse cardiac events; MI: myocardial infarction; mRS: modified Rankin scale; TIA: transient ischaemic stroke

11b Comparison of two groups in a future phase III trial: Assuming power 0.80, alpha=0.05, 1:1 randomisation, composite event rate (MACE, dementia, non-vascular death, new MRI signs) 45% and absolute reduction 9% (relative risk reduction 20%), and loss to follow-up 10%, a sample size of 1100 will be needed. A

number of outcomes are relevant to patients with SVD and using these has implications for the sample size (Table B).

Table B. Sample size for composite outcome in main trial using estimated event rates.¹

Composite model	A	B	Ci	Cil	D

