- Recruitment of sufficient patients, i.e. 400 patients in 24 months in the UK (and taking account of interruption due to COVID-19).
- >95% of randomised patients are retained for follow-up at one year.

Secondary outcomes - participant

Tolerability: 75% of patients will be able to tolerate trial medication, in at least half dose, up to one year after randomisation (i.e. less than 25% will stop trial medication completely through inability to tolerate the drugs).

Safety

- Symptoms of systemic or intracranial bleeding.
- The absolute risk of death, including fatal haemorrhage, does not differ significantly, i.e. fall outside the upper 95% CI of 2% per year on trial drugs versus no trial drugs, when given in addition to guideline stroke prevention drugs.
- There are no new ischaemic or haemorrhagic brain lesions or increase in SVD lesions on one year MRI significantly (at the p<0.01 level).

Efficacy

- Individual event-rates for stroke, TIA, myocardial ischaemia, cognitive impairment and dementia.
- The *combined rate* of recurrent stroke, MI, death, mild cognitive impairment (including dementia), dependency and new stroke lesions on scanning at 1 year will be 40-50% at one year after enrolment in order to allow detection of a modest but clinically-important reduction in poor outcomes in a phase III trial.
- Health economic measures include the health utility score (EQ-5D-5L) and the visual analogue score (EQVAS) at 12 months.

26b Units: Units will be shown in tables.

26c Calculations/transformations: Quality of life using UK weightings.

Brain frailty

Based on neuroimaging:

- Brain frailty = Atrophy + WML + Previous stroke lesion ⁷

- SVD score for CT = WML, lacunes; for MRI includes WMH, lacunes, PVS and microbleeds ¹⁵

Montreal cognitive assessment-modified (MoCA-m) trails

Since Trails A and B are performed, the MoCA trail is not collected but rather estimated from the Trails B score:

- If Trails B score <12 then MoCA trail = 0
- If Trails B score >=12 then MoCA trail = 1

27 Analysis methods

27a Methods

Primary endpoint

- Tabulation and graphical presentation of participant recruitment aiming for 400 participants in 24 months.
- Tabulation of retention of participants at one year aiming for >95%.

Analyses of secondary outcomes

Tabulations of:

- Tolerability to trial medications aiming for 75% of patients taking at least half dose for up to one year after randomisation.

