- Death, including fatal haemorrhage, aiming for less than outside the upper 95% CI of 2% per year.
- The *combined rate* of recurrent stroke, MI, death, cognitive impairment and dependency, aiming for 40-50% at one year after enrolment.

Comparison of rates of events between the treatment groups: cilostazol vs no cilostazol, ISMN vs no ISMN, and cilostazol and ISMN vs neither, for:

- Systemic or intracranial bleeding, recurrent cerebral and systemic vascular events, and vascular and non-vascular causes of death.
- Death, all cause.
- New ischaemic or haemorrhagic stroke lesion or increase in SVD lesions on MRI.
- Composite of: recurrent clinically-evident stroke, MI, death, cognitive impairment (including dementia) and dependency.
- Individual event: stroke (clinically-evident or imaging-detected ischaemic or haemorrhagic stroke to be reported separately), TIA, myocardial ischaemia, cognitive impairment and dementia.
- New infarcts and haemorrhages, absolute and change in WMH, microhaemorrhages, lacunes, atrophy imaging variables from central read of baseline imaging and one year MRI
- The comparisons of combined cilostazol and ISMN versus neither, whilst being very underpowered statistically, are presented since these may be the two groups studied in the planned follow-on trial.

Central tendency, comparisons and regressions will be analysed as follows (**Table D**).

Table D. Descriptive and analytical statistics

	Binary	Nominal	Ordinal	Continuous
Central tendency and distribution	N (%)	N (%)	Median [interquartile range]	Mean (standard deviation)
Comparisons	Chi-square (2x2)	Chi-square (2x2, or rxc)	Mann-Whitney U or Kruskal-Wallis	t-test (pooled) or 1-way ANOVA
Regression	Binary logistic regression (BLR)	-	Ordinal logistic regression (OLR)	Multiple linear regression (MLR)

27b Covariate adjustment: Analyses will be adjusted for minimisation covariates:

- Age, sex, stroke severity (NIHSS), dependency resulting from the stroke, systolic blood pressure, smoking status, time after stroke, years of education.

Covariate adjustment with continuous variables (age, NIHSS, SBP, time after stroke, years of education) will use original, not dichotomised, data.

27c Assumption checking: The assumption of proportionality will be tested using the likelihood test.

27d Alternative methods: If the data fail the assumption of proportionality (tested using the likelihood test), we will use alternative methods such as multiple logistic regression.

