27e Sensitivity analyses: In addition to assessment of raw data, the primary outcome will be analysed using additional statistical approaches in sensitivity analyses:

- Unadjusted analysis
- Imputation (multiple regression imputation) of missing data (adjusted)¹⁶

27f Subgroup analyses: The secondary endpoint of the composite of: recurrent stroke, MI, death, cognitive impairment and dependency, will be studied in:

- Pre-specified subgroups comprising the minimisation variables.
- Any other variables demonstrating imbalance at baseline.

The results of these subgroup analyses will not be adjusted for multiple testing. These analyses are planned for the phase III efficacy trial and so will be tested in the present study.

28 Missing data

Missing data may occur at outcome level or at test level or within a test at component item level. Notably, some tests have to exclude components if performed by telephone and/or postal questionnaire or require a one year MRI. There is often a relationship between inability to complete outcome assessment and cognitive function or neurological deficit after stroke (e.g. inability to hold a pen) and so assumptions around random missingness may not be valid, even if the patterns of missing data initially suggest 'missing completely at random' status. Indeed, failure to complete a test may be an indicator of cognitive impairment rather than real missingness.

The approaches taken to missing cognitive and other data can have a substantial effect on epidemiological estimates.¹⁶ We will use the approach that makes greatest use of available data.

Where in study data are not available, or participants are lost to follow-up, we have permissions to allow for linkage of the study dataset to primary and secondary care electronic health records. This will allow for an assessment of clinical outcomes across all the participants.

29 Additional analyses

Global outcomes

We will assess global outcomes integrating multiple scores into one analysis and so provide a more holistic measure and improve statistical power. We will assess global outcomes comprising:

- Recurrent ordinal stroke (clinically-evident and/or imaging-detected),¹⁷ ordinal MI, cognition (MoCA), dependency (mRS), quality of life (EQ-5D).

Analyses will use the Wei-Lachin test¹⁸⁻²¹ with comparison of data at 1 year.

Cognitive domains, based on DSM-V

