Myocardial infarction		XX (X)
Cognitive impairment		XX (X)
Dependency, mRS>2		XX (X)
Any of these	40-50%	XX (X)

Table 3. Clinical Outcomes at 12 months.

Data are number (%), median [interquartile range] or mean (standard deviation). Analyses performed using binary logistic regression (BLR), ordinal logistic regression (OLR) or multiple linear regression (MLR) with adjustment for age, sex, time from stroke onset to randomisation, years of education, smoking status, and baseline mRS (dependency), stroke severity (NIHSS) and systolic blood pressure. Mean (SD) and MLR will be used instead of median [IQR] and OLR for ordinal scales with more than 7 levels (central limit theorem/large sample). The Wei-Lachin test is used to analyse multiple outcomes in parallel.

Number	ISMN	No ISMN	Difference (p)	Cilostazol	No cilostazol	Difference (p)	ISMN + Cil	Neither	Difference (p)
Composite									
Stroke	XX (X)	XX (X)	CPHR BLR	XX (X)	XX (X)	CPHR BLR	XX (X)	XX (X)	CPHR BLR
TIA	XX (X)	XX (X)	BLR	XX (X)	XX (X)	BLR	XX (X)	XX (X)	BLR
MI	XX (X)	XX (X)	BLR	XX (X)	XX (X)	BLR	XX (X)	XX (X)	BLR
Cognitive impairment	XX (X)	XX (X)	BLR	XX (X)	XX (X)	BLR	XX (X)	XX (X)	BLR
Dependency, mRS>2	XX (X)	XX (X)	BLR	XX (X)	XX (X)	BLR	XX (X)	XX (X)	BLR
Death	XX (X)	XX (X)	BLR	XX (X)	XX (X)	BLR	XX (X)	XX (X)	BLR
Cognition									
Cognition, 7 level Normal	XX (X)	XX (X)	OLR	XX (X)	XX (X)	OLR	XX (X)	XX (X)	OLR
Minor, single domain	XX (X)	XX (X)		XX (X)	XX (X)		XX (X)	XX (X)	
Minor, multi-domain	XX (X)	XX (X)		XX (X)	XX (X)		XX (X)	XX (X)	
Major, mild	XX (X)	XX (X)		XX (X)	XX (X)		XX (X)	XX (X)	

LACI-2 SAP V1.5

06/06/2022

Major, moderate	XX (X)	XX (X)					
Major, severe	XX (X)	XX (X)					
Death	XX (X)	XX (X)					
Cognition, 4 level							
Normal	XX (X)	XX (X)					
Minor	XX (X)	XX (X)					
Dementia	XX (X)	XX (X)					
Death	XX (X)	XX (X)					
Memory/thinking problem	XX (X)	XX (X)	BLR	XX (X)	XX (X)	BLR	XX (X)
MoCA	XX (X)	XX (X)	MLR	XX (X)	XX (X)	MLR	XX (X)
TICS-m	XX (X)	XX (X)	MLR	XX (X)	XX (X)	MLR	XX (X)
Verbal fluency, animal naming	XX (X)	XX (X)	MLR	XX (X)	XX (X)	MLR	XX (X)
Trails B, time	XX (X)	XX (X)	MLR	XX (X)	XX (X)	MLR	XX (X)
Trails B, points	XX (X)	XX (X)	MLR	XX (X)	XX (X)	MLR	XX (X)
Dementia, clinical diagnosis	XX (X)	XX (X)	BLR	XX (X)	XX (X)	BLR	XX (X)
Clinical							
Systolic BP (mmHg)	XX (X)	XX (X)	MLR	XX (X)	XX (X)	MLR	XX (X)
Diastolic BP (mmHg)	XX (X)	XX (X)	MLR	XX (X)	XX (X)	MLR	XX (X)

LACI-2 SAP V1.5

06/06/2022

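### SAP: the 40-50% combined-rate target is attached to differing outcome lists (26a adds new scan lesions, Table 2 adds TIA), and 11b puts composite A's name beside composite D's 45% and 1100

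*SAP*

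**What the plan says.** **Places that carry the 40-50% target**

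- SAP 26a (Efficacy): recurrent stroke and MI, then "death, mild cognitive impairment (including dementia), dependency and new stroke lesions on scanning at 1 year will be 40-50% at one year after enrolment".
- SAP 27a (tabulations): the combined rate "of recurrent stroke, MI, death, cognitive impairment and dependency, aiming for 40-50% at one year after enrolment".
- Protocol 2.2.2: the combined rate "of recurrent stroke, MI, death, cognitive impairment and dependency will be 40-50% at one year after enrolment".
- SAP Table 2: the row *Any of these* follows stroke, TIA, myocardial infarction, cognitive impairment and "Dependency, mRS>2". Death appears in the Safety block above it.

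**Places that name a composite without a threshold**

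- SAP 27a (between-group comparisons): "Composite of: recurrent clinically-evident stroke, MI, death, cognitive impairment (including dementia) and dependency". Imaging-detected stroke is to be reported separately.
- SAP 27f: "The secondary endpoint of the composite of: recurrent stroke, MI, death, cognitive impairment and dependency, will be studied in" the listed subgroups.
- SAP Figure 2 and the block of Table 3 headed Composite: stroke, TIA, MI, cognitive impairment, dependency and death.

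**Phase III planning**

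- SAP 11b names MACE, dementia, non-vascular death and new MRI signs, with a 45% event rate, a 9-point reduction, 10% loss and a total of 1100.
- Table B (and protocol Table 7) gives that composite, column A, 50% v 40%, 950 before losses and 1250 after. It gives 45% v 36%, 976 and 1100 to column D: MACE, cognitive impairment, dependency and all-cause death.
- SAP Section 7 expects the next trial's composite to be MACE, dementia or mild cognitive impairment, non-vascular death and new MRI signs.

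**The concern.** An analyst following 26a and one following 27a would report different rates against the same target. SAP 4c ranks the SAP above the protocol, but it cannot settle a conflict inside the SAP. The lists also need different data: the 26a version needs a one-year MRI to classify anyone without a clinical event, and protocol 9.1 expects at least 15% to miss that scan. SAP 28 recognises that some outcomes depend on the MRI but gives no rule for classifying those who lack one.

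One purpose of LACI-2 is to supply event rates for phase III, and this is the rate meant to inform it. A planner who takes the composite named in 11b would read 1100 where Table B says 1250.

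**Working it through.** **1. The plan's own sample sizes.** The protocol Table 7 note states 1:1 allocation, Fleiss adjustment, alpha 5% and 10% incomplete; power is 80%. I take alpha as two-sided. Per arm, with pbar the mean of p1 and p2:

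n = [1.96 √(2·pbar·(1−pbar)) + 0.8416 √(p1(1−p1) + p2(1−p2))]² / (p1−p2)²

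n′ = (n/4)·[1 + √(1 + 4/(n·|p1−p2|))]², rounded up and doubled.

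| Column | Rates | Recomputed | Stated | Recomputed /0.90 | Stated total |
|---|---|---|---|---|---|
| A | 50 v 40% | 816 | 950 | 907 | 1250 |
| B | 10 v 8% | 6626 | 6626 | 7363 | 7400 |
| Ci | 30 v 24% | 1784 | 1784 | 1983 | 2000 |
| Cii | 30 v 21% | 778 | 778 | 865 | 900 |
| D | 45 v 36% | 976 | 976 | 1085 | 1100 |

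Four columns match exactly before losses, which supports the method and the two-sided alpha. Column A does not match. From its stated 950, 10% loss gives 950/0.90 = 1,056. Adding 15% missed MRI gives 950/(0.90 × 0.85) = 1,242, close to 1250, but neither table states that allowance. From 816, both allowances give 816/(0.90 × 0.85) = 1,067.

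The 1100 in 11b is therefore sound for D. The error is the composite named beside it.

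**2. Rate under the list without scan lesions.** Inputs from SAP Table A: MI 0.6%; death 1.8 + 0.5 = 2.3%; dependency 15%; intracerebral haemorrhage 0.5%; and 2.5% for "Non-fatal IS or TIA". Because that 2.5% is joint, the stroke rate s lies between 0.5% (all of it TIA) and 3.0% (all of it stroke). Components are assumed independent, and c is the cognitive impairment rate:

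Rate = 1 − (1−s)(1−0.006)(1−0.023)(1−c)(1−0.15)

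- c = 30% (Table A): 42.5% to 44.0%.
- c = 16% (new impairment at one year, protocol 9.1): 31.0% to 32.7%.

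**3. Adding scan lesions.** The documents give no new-lesion rate L. With independence, rate = 1 − (1 − rate from step 2)(1 − L):

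| Assumed L | c = 30% | c = 16% |
|---|---|---|
| 5% | 45.4-46.8% | 34.5-36.1% |
| 10% | 48.3-49.6% | 37.9-39.5% |
| 15% | 51.1-52.4% | 41.4-42.8% |
| 20% | 54.0-55.2% | 44.8-46.2% |

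At c = 30% the result reaches 50% when L = 1 − 0.50/0.5605 = 10.8% to 1 − 0.50/0.5749 = 13.0%. At c = 16% it reaches 40% when L = 1 − 0.60/0.6726 = 10.8% to 1 − 0.60/0.6899 = 13.0%.

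SAP Section 7 says the components are likely to be correlated. If a share q of participants with new lesions already count under the other components, the crossing is L = (limit − rate)/(1 − q). With q = 60% this is 15.1-18.7% at c = 30% (limit 50%) and 18.1-22.5% at c = 16% (limit 40%). With q = 80% and c = 30% it is 30.2-37.5%.

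**4. TIA and death in Table 2 (c = 30%).** Counting TIA sets s = 3.0%. Without death the rate is 1 − 0.97 × 0.994 × 0.70 × 0.85 = 42.6%; with death it is 44.0%. Against 42.5-44.0% the shift is −1.3 to +0.1 points, or 0 to +1.4 points.

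**5. Missing MRI.** With 15% missing, 60 of 400 lack a scan. At a 42.5-44.0% clinical rate about 26 of them already have a qualifying event. About 34 are undetermined, and about 366 have known status. This assumes missing MRI is unrelated to events.

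**The case against.** **26a may be what was intended.** A reader might infer that 26a is simply a slip. The documents do not support that: Section 7 and 11b also put new MRI signs in the phase III composite, and 26a ties its target to a phase III trial. The 27a tabulation says recurrent stroke without qualification, and the SAP elsewhere uses stroke to cover imaging-detected events. So the 27a tabulation does not list scan lesions, which is less than saying it excludes them. This stands. The finding is a conflict, not a proven error in one place.

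**The definition may not change the answer.** A reader might infer that 26a pushes the rate above 50%. That depends on an assumed lesion rate, the choice between 30% and 16% impairment, and overlap between components. With 16% the same lesion rate brings a low result up into the band instead. This also stands.

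**The MRI need not shrink the denominator to those scanned.** A reader might infer that at most 340 of 400 could be classified. A participant with a clinical event is positive without a scan, so only those with neither are undetermined.

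**Column A was not adopted.** Protocol 9.1 says an MRI-based outcome was considered and gives reasons against it, including missed scans. That makes column A less important and explains most of the step from 950 to 1250. It does not explain 950 against 816.

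**Conclusion.** The inconsistency is real. One stated target is attached to lists that differ on scan lesions, TIA and the placing of death. Whether Table 2 counts death is itself unclear: its dependency row could take in mRS 6, but Table A defines dependency as mRS 3-5 and Table 3 has a separate death row.

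The scan-lesion difference could move the reported rate across a limit of the target band, in a direction that depends on the cognitive impairment rate. Neither crossing is established. The Table 2 difference is under 2 points under the Table A assumptions. The 11b label contradicts Table B, and column A's 950 is not reproducible from its stated inputs.

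A reader might infer that the LACI-2 sample size or its primary result is in doubt. It is not: the 400 rests on the death rate, the primary endpoint is recruitment and retention, and no go/no-go rule uses the combined rate. What is affected is a descriptive secondary target and phase III planning.

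**What to change.** Before final lock:

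- Attach the 40-50% target to one list and use that list in 26a, 27a, 27f, Table 2, Table 3 and Figure 2. The natural choice is recurrent clinically-evident stroke, MI, death, cognitive impairment including dementia, and dependency, because 27a, 27f and protocol 2.2.2 already use those components. State that death is counted, and report TIA separately.
- Report the version with new MRI lesions as a separately labelled rate, since Section 7 names new MRI signs for the likely phase III composite. State how participants without a one-year MRI are classified, distinguishing those with a clinical event from those without.
- In 11b make the name and the figures agree with Table B: composite D with 45% and 1100, or composite A with its own corrected figures.
- In Table B and protocol Table 7 correct column A's size or its inputs, and state the loss and missing-MRI allowance used.

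The cost is SAP wording, the Table 2, Table 3 and Figure 2 shells, one label and one table column. No new data are needed.

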5.5 RANDOMISATION

5.5.1 Randomisation Procedures

The electronic randomisation system and trial database are hosted by the University of Nottingham. Randomisation involves minimisation on key prognostic factors including: age, sex, stroke severity (NIHSS), dependency resulting from the stroke, systolic blood pressure $\leq/ > 140$, smoker status, time after stroke, years of education. Years of education give an estimate of pre-morbid cognitive ability and predicts post-stroke cognitive impairment; BP and smoking predict recurrent stroke; delay since stroke reflects disease activity; age, sex and stroke severity are standard minimisation variables. This approach ensures concealment of allocation (note allocation concealment means that it is not possible to guess which treatment the next patient will be randomised to), minimises differences in key baseline prognostic variables, and improves statistical power. Randomisation will not be minimised by Centre because this may result in high rates of allocation prediction, but a pre-specified post-hoc analysis by centre will be performed to investigate and adjust for heterogeneity of treatment effect by centre.

Randomisation will allocate a trial treatment, which will be prepared by the local participating Pharmacy.

Note that randomisation will be performed during normal office hours (09.00 – 17.00) and the trial allows for randomisation to occur months or years after the stroke. Therefore, in the event of computer failure (for example: server failure), the investigator will wait until the computer system is re-established to perform the randomisation. Normally, this would only be a few minutes to two hours. However, if this delay requires the patient to return on a separate occasion to collect the drugs, then a separate appointment will be made and the patient's travel expenses covered as per other trial visits.

Patients will be randomised to one of the following at a 1:1 ratio as per Section 6.2:

- cilostazol versus no cilostazol
- isosorbide mononitrate versus no isosorbide mononitrate

resulting in a partial factorial comparison of cilostazol versus isosorbide mononitrate versus both drugs versus neither drug.

The randomisation algorithm will allocate a unique identifier which will be used to label the treatment pack containing the appropriate drug made up for the patient and dispensed by the local Pharmacy.

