9 STATISTICS AND DATA ANALYSIS

9.1 SAMPLE SIZE CALCULATION

There are few data on which to base sample size. There is little experience with cilostazol in Europe or North America, and little experience with ISMN in this group of patients in the UK (or in any patients with stroke). We have been guided by colleagues in Japan where cilostazol is in common use and there is experience with it in stroke. The main purposes of the trial are to assess tolerability and safety.

Table 6 Annual absolute risks (%) of outcome events after lacunar stroke

Vascular death	Non-vasc death	Non-fatal isch stroke or TIA	Non-fatal ICH	MI	MACE	Dependent (mRS 3-5)	Any cogn impt.	Dementia
1.8	0.5	2.5	0.5	0.6	3	15	30	15

We calculated mean annual event rates (Table 6) from trials (SPS3,³³ lacunar patients in ENOS⁵⁰ IST-3,⁶³ of cilostazol, Figure 1) and observational data (LADIS;⁶⁴ our^{4, 65} and other⁶⁶

studies). We expect deaths including vascular deaths of median 2.0% p.a., with 4% being the upper 95% CI of 2% in 400 patients.³³ LACI-2 therefore has a sample size of 400.

For a main Phase III trial, recurrent stroke 2.5%pa, MI 0.6%pa and vascular death 1.8%pa,^{4, 33} (MACE) are infrequent; new cognitive impairment c16% at one year,^{6, 66} dependency 15%, are frequent and important to patients, justifying their inclusion in a composite primary outcome. However, these event rates are imprecise with wide ranges; more precise estimates are needed. We estimate main Phase III trial sample size at 1100 (Table 7), assuming 80% power, alpha 5%, 10% loss to follow-up, composite event rate (45%) and conservative estimate of cilostazol effect (20% RRR is the lower 95% CI of effect, Figure 1). A primary outcome including MRI SVD progression (A, below) was considered but at least 15% of patients miss repeat MRI, sample sizes were similar (or larger, due to variance in WMH change⁶⁵ short term), the cost is much higher and the WMH intermediary measure is less relevant to patients.

Table 7. Sample size for composite outcome in main trial, estimated event rates.

Composite model	A	B	Ci	Cii	D
Composite outcome for Phase III includes:	MACE, dementia, non-vasc death, new MR signs	MACE, dementia, death	MACE, cog↓, dependency↓, death		MACE, cog imp, depend, all death
1-beta (power)	80%	80%	80%	80%	80%
Event rate, control, pa	50%	10%	30%	30%	45%
Relative risk reduction	20%	20%	20%	30%	20%
Event rate, active, pa	40%	8%	24%	21%	36%
Total sample size	950	6626	1784	778	976

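### The 40-50% combined-rate criterion rests on a Phase III control rate but names no arm; read on all arms pooled, an effective drug lowers the chance of meeting it

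*SAP*

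**What the plan says.** Protocol 2.2.2 sets the combined rate of recurrent stroke, MI, death, cognitive impairment and dependency as a secondary efficacy endpoint that "will be 40-50% at one year after enrolment in order to detect modest but clinically-important reductions in poor outcomes". SAP 26a repeats the range and gives its purpose for Phase III: "will be 40-50% at one year after enrolment in order to allow detection of a modest but clinically-important reduction in poor outcomes". SAP 27a lists it among the tabulations, "aiming for 40-50% at one year after enrolment", apart from the list of between-group comparisons that follows. SAP Table 2 has a single column for what was achieved. The combined-rate row shows 40-50% with no split by arm, whereas tolerability in the same table has a row for each active regimen.

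The Phase III sizing in protocol 9.1 assumes "composite event rate (45%) and conservative estimate of cilostazol effect (20% RRR is the lower 95% CI of effect, Figure 1"). In protocol Table 7 the 45% (model D) stands in the row "Event rate, control, pa", against 36% on active treatment. SAP 11b gives the same rate and result: "45% and absolute reduction 9% (relative risk reduction 20%), and loss to follow-up 10%, a sample size of 1100 will be needed".

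Protocol 5.5.1 randomises each drug 1:1 against no drug, giving a partial factorial comparison of "cilostazol versus isosorbide mononitrate versus both drugs versus neither drug". Protocol section 3 lets patients with a contraindication to one drug be randomised on the other drug only.

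**The concern.** A rate from which a reduction is to be detected is an untreated rate, and the plan's own sizing table labels it so. The criterion is set against a figure with no arm attached, in a trial where most participants are allocated at least one active drug. The threshold and the observed figure then measure different things, and they part whenever either drug has an effect.

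Two consequences follow. A beneficial drug pulls the pooled rate towards or below 40% although the control rate is as planned, so treatments that do nothing have the best chance of meeting the criterion. In the other direction, benefit can bring a control rate above 50% back inside the range. Outcome event rates are a stated secondary objective (SAP 8b), and protocol 9.1 says that the existing rates are imprecise and that better ones are needed, so it matters which rate is reported against the target.

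**Working it through.** **Inputs.** Control rate 45%, RRR 20%, power 80%, alpha 5% (taken as two-sided), 1:1 allocation, Fleiss correction (protocol 9.1 and Table 7; SAP 11b). Control rate 50% for model A, which includes new MR signs. 363 recruited (SAP Table 2). 1:1 randomisation for each drug (protocol 5.5.1). My assumptions are four equal arms and, in some rows, a 20% RRR for ISMN.

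**The plan's own figure.** For 45% v 36%, the mean rate is 0.405 and the difference 0.09.

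n per arm = [1.960·√(2×0.405×0.595) + 0.842·√(0.45×0.55 + 0.36×0.64)]² / 0.09² = 465.8.

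Fleiss correction: (465.8/4)·[1 + √(1 + 4/(465.8×0.09))]² = 487.8, rounded up to 488. The total is 976, as the plan states. Dividing by 0.9 gives 1,085, close to the plan's 1,100. The 45% is therefore used as a control-arm rate.

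**Expected pooled rate.** Pooled rate = control rate × mean of the four arm multipliers (neither, ISMN, cilostazol, both). The last column is the exact binomial chance that 146 to 181 of 363 participants, that is 40-50%, have the outcome.

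| Control rate | Scenario at 20% RRR | Multipliers | Pooled rate | Chance of 40-50% |
|---|---|---|---|---|
| 45% | Neither drug works | 1, 1, 1, 1 | 45% | 94% |
| 45% | Cilostazol only | 1, 1, 0.8, 0.8 | 40.5% | 56% |
| 45% | Both, no extra gain from the combination | 1, 0.8, 0.8, 0.8 | 38.25% | 24% |
| 45% | Both, multiplicative | 1, 0.8, 0.8, 0.64 | 36.45% | 8% |
| 45% | Both, additive | 1, 0.8, 0.8, 0.6 | 36.0% | 5% |
| 50% | Both, no extra gain | 1, 0.8, 0.8, 0.8 | 42.5% | 82% |
| 50% | Both, multiplicative | 1, 0.8, 0.8, 0.64 | 40.5% | 56% |
| 50% | Both, additive | 1, 0.8, 0.8, 0.6 | 40.0% | 49% |

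**Break-even.** At a 45% control rate the expected pooled rate reaches 40% when the RRR is 22.2% (cilostazol only), 14.8% (both, no extra gain) or 11.4% (both, multiplicative).

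**Masking.** A 55% control rate with both drugs at 20%, multiplicative, pools to 0.55 × 0.81 = 44.6%. The chance of observing 40-50% is then about 94%, although the control rate lies outside the range.

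**Single-drug entry.** The documents do not give the number randomised on one drug only. If it is 5-30% (assumed), the share allocated a drug falls from 75% to 74-68%. With both drugs working at a 45% control rate, the pooled rate is then 36.6-38.9% (multiplicative or no extra gain).

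**Precision.** The 95% half-width at 45% is 1.96·√(0.45×0.55/n). This is 5.1 points for n = 363 and 10.2 points for n = 91 (363/4, assuming full factorial entry).

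**Illustration only.** If a pooled rate were carried forward as the control rate with a 20% RRR, the same formula gives 1,156 (40.5%), 1,262 (38.25%) or 1,356 (36.45%) before losses, instead of 976.

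**The case against.** The strongest reply is that the information is already planned. SAP 27a compares a clinical composite for each drug against none and for both drugs against neither. It explains that the last pair may be the groups in the follow-on trial. SAP Table 3 has a column for the neither group. The criterion is also secondary: the primary endpoint is recruitment and retention, and no go or no-go rule hangs on the event rate. All of this stands. It means that the untreated rate can be obtained, but the criterion is still not tied to it.

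A reader might infer three stronger things that the documents do not support.

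- **That the criterion fails if the drugs work as the plan assumes.** The plan justifies the 20% for cilostazol only, as a "conservative estimate of cilostazol effect (20% RRR is the lower 95% CI of effect, Figure 1"). On that basis the expected pooled rate is 40.5%, which passes narrowly. Falling below 40% needs an ISMN effect that the plan never states, and also a control rate below about 47-50% (0.40 divided by the mean multiplier: 0.85, 0.81 or 0.80). The relevant control rate is itself uncertain: SAP 26a counts new lesions on scanning, and the tabulated model with new MR signs is A, at 50%.
- **That the plan says the rate is pooled.** No sentence does. Pooling is inferred from the layout of Table 2 and SAP 27a.
- **That Phase III will be wrongly sized.** Nothing says that a pooled rate will be used as the Phase III control rate.

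**Conclusion.** The point holds as a mismatch between the threshold and the quantity reported against it. The 40-50% criterion serves a calculation based on an untreated rate, and the plan reports it without an arm, so it is naturally read on a mostly treated population. At a 45% control rate and n = 363, effective treatment cuts the chance of meeting it from about 94% to 56% under the effect that the plan does assume. The chance falls to 5-24% if ISMN were equally effective.

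This rests on equal arms, on the 45% rate applying to the composite that is tabulated, and on the pooled reading of Table 2. At a 50% control rate the expected pooled rate remains in range. The finding is therefore that benefit works against the criterion and that pooling can mask a high control rate; certain failure does not follow. It should be corrected, but it does not affect the primary endpoint.

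**What to change.** 1. In SAP 26a and 27a, state that 40-50% refers to the rate in participants allocated neither drug.
2. In Table 2, set the observed neither-arm rate with its 95% CI against the criterion. Keep the pooled rate as a descriptive row only.
3. State that the untreated rate will be used for Phase III sizing.
4. Optionally, add as a supporting estimate an untreated rate standardised over all participants from a logistic model with both drug terms and the minimisation variables. Say that it assumes no cilostazol-by-ISMN interaction, and show the result with the interaction term as well.
5. Use one composite for the criterion. SAP 26a adds new lesions on scanning, the 27a tabulation does not, and Table 2 adds TIA and has no death row among the efficacy components. SAP 11b also pairs 45% with model A's components, whereas Table B gives 45% for model D.

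The cost is SAP wording, one table row and, if wanted, one model output; no new data are needed. The real downside is precision: about ±10 points in about 91 neither-arm participants, against about ±5 pooled. That interval is wider than the 40-50% window itself, and at a true 45% the point estimate from 91 people falls inside the window only about 66% of the time. The interval should therefore be read with the estimate. The narrower pooled interval describes a different quantity.
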